Figure 1| Metabolism of 3 ketone ester compounds and the BDO ketone-precursor.

IMPACT

KEs could represent a practical STAK method that does not require any change in diet. However, there is a critical need to elucidate unique attributes of the many new exogenous ketone compounds and how their metabolism varies between individuals to inform KE use in the field. This high impact project will contribute important knowledge that aims to develop next-generation KE molecules and formulations that are designed to meet the needs of operators at different points in their career. Our long-term goal is to create evidence-based guidelines for deployment of diverse KE compounds, dose level, and timing based on individual characteristics and operational/training requirements.

RESEARCH STRATEGY

This is an open label, randomized, placebo controlled, 9-arm crossover study where healthy adult men (n = 15) will consume four different exogenous ketone products at two serving sizes or a non-ketogenic placebo (one study product per test day). Data/sample collection will include blood (capillary and whole venous blood), gas exchange measures, urine, heart rate/variability and study product tolerability.

OUTCOMES

Primary

- Difference in total plasma ketone appearance (AUC) between the two serving sizes of study products and control

Secondary*

- Differences in other blood ketone kinetic parameters (peak concentration, time of peak concentration, AUC of different ketone bodies, capillary ketone concentrations).
- Differences in urine and breath ketone excretion
- Differences in blood metabolites (glucose, free fatty acids, alanine).
- Differences in heart rate and heart rate variability and blood pressure
- Differences in subjective tolerability and subjective satiety measured by questionnaires
- Differences in blood hormones (insulin, ghrelin).
- Differences in blood acid-base balance (bicarbonate, strong ions
- Differences in respiratory gas exchange (VO₂ and VCO₂)

*All comparisons will be made between the two serving sizes of one study product and vs. control.

PARTICIPANTS

This study aims to recruit a homogenous, military relevant population to remove the confounding effects of variation in phenotype on exogenous ketone metabolism as far as possible. Thus, we will 15 recruit healthy and normally-active resistance/endurance trained men from the ages of 20-30 yr that represents typical active-duty military

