bowel disease, irritable bowel syndrome, chronic constipation, severe constipation (in the opinion of the Investigator), history of frequent diarrhea, history of surgery for weight loss, gastroparesis, systemic disease that might affect gut motility according to the Investigator, medication managed reflux and/or clinically important lactose intolerance].

- Participant has a condition the Investigator believes would interfere with his ability to provide informed consent, comply with the study protocol, which might confound the interpretation of the study results, or put the participant at undue risk.

Sample Size. Our primary outcome goal is to demonstrate significant differences between serving sizes of exogenous ketone compounds in plasma total ketone AUC. Previous work using the BHB Monoester compared to ketone salt products demonstrated that a sample size of 12 participants was required to detect a difference in BHB AUC of ~20% (80 mM.h⁻¹) between ketone compounds with alpha set at 0.5 and power at 0.8. This sample size will also give sufficient power to address our secondary aims which include differences in peak ketone concentrations, plasma BHB, AcAc, breath acetone, glucose, insulin, free-fatty acids, amino acids, blood chemistry, pH, gas exchange values and heart rate. Based upon prior studies, we expect up to 20% of participants will withdraw from the study after recruitment, and therefore we will plan to recruit 15 participants.

Recruitment:

Recruitment will occur through well-established methods at OSU, which include word of mouth, ResearchMatch database, social media engagement and flyers. For this study we will specifically aim to recruit cadets in the OSU Reserve Officers Training Corps (ROTC), who have participated in research on ketosis in the past and been supported by their cadre to enroll in our research projects (see letters of support from Army, Navy, and Air Force ROTC leadership).

Randomization:

If a participant meets all inclusion and none of the exclusion criteria, the following will occur at the end of the screening visit:

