- The randomization sequence will be prepared using an online random sequence generator (randomization.com) that will generate a list of random number sequences between 1 – 9 that correspond to product/serving code. If a participant meets all inclusion and none of the exclusion, a staff member will randomize the participant – in the order that they are enrolled. The randomization number will be recorded in the participant's source documentation.

METHODS

Study overview:

[figure not shown]

Figure 2 | Study schematic, showing timeline for a study day.

Study Procedures

Study Day	Screening	Test Days 1-9
Visit to Study Center	X	X
Informed consent	X	
Medical intake questionnaire, taste screening, diet assessment, anthropometrics ¹	X	
Randomization ²	X	
Compliance assessment ³		X
Consume study product ⁴		X
IV Cannulation and whole blood collection ⁵		X
Urine collection ⁶		X
Respiratory gas analysis ⁷		X
Heart rate and HRV monitoring ⁸		X
Tolerability assessment ⁹		X
Satiety assessment ¹⁰		X
Continuous Ketone Monitor placement/check ¹¹		X

1. Medical intake questionnaire, taste screening diet assessment questionnaire and anthropometric data will include: Lean Body Mass by DXA, BMI, height and weight.
2. Order of study products will be randomized using a computer randomization generator.
3. Prior to starting each test day, you will be asked to confirm that you meet pre-test criteria, including: fasted >10 h, no alcohol for 24h, no exercise for 24h and consumed the provided pre-test food.

4. Study Product will be consumed within +/- 60 minutes of the time established on the first test day. Participants will be provided with a choice of non-caffeinated, non-caloric beverage to remove the bitter taste of the Study Product.
5. IV cannula will be inserted at the start of each Test Day, and removed at the end of each Test Day. Blood samples will be collected according to the schedule in Figure 1. Cannula will be flushed with a small volume of saline after each sample to maintain patency. We will draw 504 mL of blood, which is about 2.1 cups throughout the 4-week intervention.

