NJ, USA) and ‘Avela’ (Genomatica, CA, USA), respectively. The AcAc Diester is commercially available (on Amazon <https://www.amazon.com/KetoLogic-Ketone-DiEster-Softgels>) and is currently being used in clinical studies of Angelman’s Disease²¹. We have been in communication with the companies that produce these exogenous ketones to ensure product availability and support for this work (see letters of support from BHB Therapeutics/Juvenescence and Disruptive Nutrition).

Quality Control: As only small amounts of product are needed for this study, and products are shelf stable, our aim is that all product inventory will be acquired at the start of the study to ensure the same product lots are used throughout. We plan to obtain Certificates of Analysis to confirm product exogenous ketone content.

Serving Size Rationale: Previous work has shown that lean body mass (LBM) is a major covariate in KE responsiveness⁹. Therefore, we will standardize exogenous ketone serving sizes to LBM (assessed using DXA) for all trials at 180 and 360 mg/kg LBM, which for a participant with 70 kg of lean mass corresponds to ~12.5 and 25 g, respectively. These serving sizes are representative of typical commercial serving sizes and are expected to elevate blood BHB in the range of 1.5 - 2 mM^{22,23}.

Blinding: It will not be possible to completely blind study participants or investigators due to visible differences between the C6 Ketone Di-ester and BHB-Mono-ester beverages and also the capsule delivery form for the AcAc Di-ester. However, study products will be coded (A, B, C, D and CON), and data analysts will remain blinded to the coding until analysis is complete.

Storage: The study products will be stored in a dry secure location at ambient temperature (15- 77°F) and are best served chilled. Study product supplies are to be used only in accordance with this protocol and under the supervision of the Investigator.

Table 1: Study product details

Study Active Ingredient	Serving Sizes	Form	Other product ingredients [ALLERGENS]	Example Commercial Product (Company)
BHB Mono-ester	180 mg/kg and 360 mg/kg	Ready to drink beverage	Water	DeltaG Tactical (TDeltaS Global, FL, USA)

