Statistical Plan. Statistical analysis of data will take place on completion of the study in collaboration with Buck Bioinformatics Core. Participant data will be included if they have completed at least 2 serving sizes of one exogenous ketone product AND the control Test Days (i.e., BHB- mono-ester 180 mg/kg, BHB mono-ester 360 mg/kg and Control). Any incomplete exogenous ketone compounds (i.e., participant completed C6 Di-ester 180 m/kg and AcAc ester at 360 mg/kg) will be excluded from the analysis. All decisions regarding exclusion from the analysis population will be documented prior to database lock. Missing data will not be imputed, and only observed data will be included in the statistical analysis.

Repeated measure group x time ANOVA (or a non-parametric alternative) will be performed following initial tests to ensure sphericity is not violated. We will compare data between control group vs. each individual exogenous ketone at both doses (i.e., control vs BHB-mono ester (180 mg/kg) vs BHB-mono-ester (360 mg/kg). We will also test for condition x time interactions. If significance is detected, post-hoc comparisons will be made using Tukey's HSD tests (or non-parametric alternative) to correct for multiple comparisons. Significance will be accepted at an alpha level of P < 0.05.

Other data processing:

- Area Under the Curve (AUC) will be calculated using the Trapezoid Rule.
- Maximal/minimal concentration data (C_{max} and C_{min}) and time of maximal/minimal concentration (T_{max} and T_{min}) will be extracted from the raw data.

- A composite tolerability score is calculated by adding the scores (0 -3, corresponding to none, mild, moderate, severe) of all ten listed symptoms.

STUDY MONITORING

Concomitant Medication/Supplements and Treatment

All concomitant medications/supplements used 1 months prior to Screening Visit and during the study will be reported to the study personnel for assessment and recorded in the participant's study documents.

Adverse Event Monitoring

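### The ANOVA is made conditional on a sphericity pre-test that cannot ensure sphericity with 12 participants; it should be replaced by a correction that is always applied

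*Protocol*

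**What the plan says.** All references are to the Protocol.

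- **Statistical Plan, model:** "Repeated measure group x time ANOVA (or a non-parametric alternative) will be performed following initial tests to ensure sphericity is not violated". No epsilon correction is named, and neither is the action after a failed test.
- **Statistical Plan, comparisons:** "We will compare data between control group vs. each individual exogenous ketone at both doses", so there are three conditions per product. The plan also tests the condition-by-time interaction.
- **Statistical Plan, post-hoc:** Tukey's "HSD tests (or non-parametric alternative) to correct for multiple comparisons".
- **Sample Size:** "Our primary outcome goal is to demonstrate significant differences between serving sizes of exogenous ketone compounds in plasma total ketone AUC". It plans 15 recruits to allow for 20% withdrawal; the Study Synopsis gives 12 evaluable.
- **Research Strategy:** participants take four products at "two serving sizes or a non-ketogenic placebo (one study product per test day").
- **Serving Size Rationale:** the servings are "expected to elevate blood BHB in the range of 1.5 - 2 mM".
- **Randomization:** an online generator will "generate a list of random number sequences between" 1 and 9. No balancing over test days is described, and the stated model has no test-day term. The nine days are spread "throughout the 4-week intervention" according to the Study Procedures notes, or over 6 weeks according to Continuous Ketone Monitoring.

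**The concern.** Sphericity means that all pairwise differences between conditions have the same variance. There is reason to doubt it here: control is non-ketogenic and should give AUCs close to baseline in everyone, while the two servings raise ketones by different amounts, so the spread may well grow from control to 180 to 360 mg/kg. A non-significant pre-test in 12 people is weak evidence against this. The plan then proceeds with an uncorrected F test in just those datasets where the departure was missed. When the pre-test does reject, the plan leaves the next step open, although that step affects the comparison named as the goal, 180 against 360 mg/kg.

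A lesser issue is test-day order. With plain random orders and no test-day term, any drift over the nine days goes into the error term.

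**Working it through.** **Inputs from the protocol.** 12 evaluable, 15 recruited: 12/(1 - 0.20) = 15, which reproduces. Three conditions per product; 7 blood samples per test day (Testing Days); alpha 0.05 (Statistical Plan). AUC has one value per test day, so for the primary outcome sphericity concerns only the three conditions.

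**Assumed.** AUC SDs for control:180:360 of 1:2:3 or 0.2:1:2, normal and uncorrelated (a within-person correlation of 0.5 barely changes the results). Mauchly's test at 5% stands for the unnamed pre-test.

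**1. Size of the departure.** With variances s, epsilon = [(2/3)Σs]² / {2[Σs²/3 + (Σs)²/9]}.
- 1:2:3 (s = 1, 4, 9): 9.333² / [2(32.67 + 21.78)] = 0.80.
- 0.2:1:2 (s = 0.04, 1, 4): 3.36² / [2(5.667 + 2.822)] = 0.665.

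**2. The pre-test and what follows.** Simulation at n = 12 with no true difference, using the exact Mauchly p = W^5:

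| | 1:2:3 | 0.2:1:2 |
|---|---|---|
| Mauchly rejects | 29% | 68% |
| Departure missed | 71% | 32% |
| F-test error after a pass | 6.8% | 10.8% |
| Whole procedure, Greenhouse-Geisser after a fail | about 5.5% | about 5.5% |
| Whole procedure, Friedman after a fail | 6.4% | 6.9-7.0% |
| Greenhouse-Geisser always, no pre-test | 4.7% | 4.9-5.0% |

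If the SDs are equal, always correcting gives 4.1-4.2%.

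**3. Post-hoc pairs.** Tukey's test with pooled error has 2.0% error for 180 vs 360 mg/kg under equal SDs. With equal 180 and 360 means it has 4.6% or 5.8% under the two unequal patterns. An epsilon correction changes the omnibus F only and does not repair this.

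**4. Condition-by-time pre-test (secondary).** Contrasts: (3 - 1)(7 - 1) = 12. Degrees of freedom at n = 12: 11. The 12 x 12 contrast covariance has rank 11, so its determinant is zero and Mauchly's test cannot be computed. At n = 13 it has full rank.

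**5. One possible fallback.** If control is lowest in everyone and m of n participants are higher at 360 than at 180 mg/kg, the mean-rank difference is (2m - n)/n, at most 1. At n = 12 the critical differences are:
- Nemenyi: (3.314/√2) x √(12/72) = 0.957.
- Dunn: 2.394 x √(12/72) = 0.977.

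With m = 11 the difference is 10/12 = 0.833, so all 12 must be higher. The same holds for all participants at n = 13 and 14. For a true effect of e SDs of the paired difference, the chance of this is about Φ(e)^12: 12% at e = 0.98, 76% at 2, 93% at 2.5, 98% at 3. At e = 0.98 the power of the whole procedure is 65% or 35%, against 89% or 90% for Tukey's test with no pre-test. With Wilcoxon tests and Holm's adjustment as the fallback it is 86% or 84%.

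**6. Test-day drift (assumed linear, from -d to +d SD over nine days).** The days of two conditions differ with variance 15, so the variance of a paired difference grows by the factor 1 + (d/4)² x 15/2: 1.03, 1.12 and 1.47 at d = 0.25, 0.5 and 1. For an effect of 1.381 SD (80% power without drift, equal SDs, Tukey):

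| d | 0 | 0.25 | 0.5 | 1 |
|---|---|---|---|---|
| As written | 80% | 79% | 75% | 61% |
| Random orders + covariate | 78% | 78% | 78% | 77% |
| Balanced orders + covariate | 79% | 79% | 79% | 79% |

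Error as written stays at its 2% per-pair level throughout.

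**The case against.** **The statistical analysis plan may settle this.** It is not shown, and it could name an epsilon correction, the fallback and a test-day term. That stands for the missing details. It does not cover the pre-test, which the protocol itself lays down.

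**The harm is small.** This stands in part. Overall error is about 5.5% to 7%, and the 11% figure applies only to the 32% of trials that pass under the more extreme pattern. The SD patterns are assumed; the protocol gives expected concentrations, not variances.

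**A reader might infer that the pre-test has little power in general.** It does not: 68% rejection at epsilon 0.665 is substantial. Low power holds for mild to moderate departures, such as 29% at epsilon 0.80.

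**A reader might infer that the plan cuts power for 180 vs 360 mg/kg to 65% or 35%.** The text does not support that. It does not say that a failed sphericity test, rather than non-normality, leads to ranks, nor does it name Nemenyi or Dunn. The figure also needs an effect of only 0.98 SD. A twofold serving difference may be much larger, and part of the 89-90% comparator comes from a Tukey test that is liberal under those SDs.

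**A reader might infer that random orders without a test-day term bias the comparison.** They do not: random ordering is valid and the error rate holds. No section predicts drift, and fasting, diet and exercise rules, a fixed ingestion time and an aim of single product lots limit it. If 1.381 SD is read as the 20% difference in Sample Size, one SD is 20/1.381 = 14.5% of AUC, and the fall to 61% needs a steady 29% change from first to last day.

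**The uncomputable pre-test** arises only at exactly 12 evaluable and concerns a secondary test. That is right.

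**Conclusion.** The point holds for the sphericity pre-test. As stated it cannot do what it is meant to do with 12 participants. Under the assumed SD patterns it passes 71% or 32% of the time, and the F test then has about 7% or 11% error. The whole procedure has about 5.5% to 7%, depending on a fallback that the protocol leaves open. That open choice is a risk for the 180 vs 360 mg/kg comparison, not a demonstrated loss: some rank methods would need all 12 participants to agree, others lose little. The condition-by-time pre-test fails outright only if exactly 12 are evaluable.

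The test-day part is a secondary matter of precision, not validity. It gains materially only if drift is large. Its one time-critical element is the order list, which cannot be rebalanced once participants are enrolled.

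Overall: a change that should be made because it is simple and nearly free, not because the trial is invalid without it. Confidence is medium, since every size rests on assumed SDs or drift.

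**What to change.** **Main change, Statistical Plan.** Delete the condition that sphericity be tested first. For AUC, compare control, 180 and 360 mg/kg for each product with a repeated-measures ANOVA that always carries the Greenhouse-Geisser correction. After a significant result, test each pair on its own paired differences at 5%; with three conditions this holds the familywise error at 5%. A mixed model with a separate variance per condition is an equal alternative. For the time profiles, also apply the correction without a pre-test; with seven time points at n = 12 its error was 2.2-4.5% in simulation, so it is on the cautious side.

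**Secondary change, before first enrolment.** Draw the orders from a randomised Williams-type 9 x 9 square, with its mirror square for participants 10-15, and add test-day number as a 1-df within-participant covariate. With paired differences, regress each on the difference in test-day number. A joint nine-condition model is not needed.

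**Cost.** Two or three sentences and a different sequence list; no extra data. The omnibus test is slightly conservative if SDs are equal (about 4.2%). Without drift the covariate costs about 1 point of power with balanced orders, or 2-3 with random ones. Balance is only partial at 12-15 participants: the SD of the difference in mean test day between 180 and 360 mg/kg falls from 1.12 to 0.65 days with 12 of 15 evaluable. A linear term also helps less if drift is not linear: for a 2-SD shift on day 1 only, power is 63% as written and 67% with the change.

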KE Metabolic Effects Vary Between Compounds. One important difference between KE compounds is the ketone-promoting components, which determines the circulating ratio of blood ketone bodies, BHB and AcAc, and may in turn lead to important metabolic and signaling differences. Whereas some actions of the ketone bodies BHB and AcAc are shared, R-BHB has a broad range of signaling functions that are distinct from AcAc, some of which are shared by the non-circulating, non-oxidizable enantiomer, S-BHB^{13,14}. AcAc also has metabolic and signaling actions that are independent of BHB¹⁵⁻¹⁸ and is selectively oxidized in some cells that cannot oxidize BHB⁴². Furthermore, responses to different ketone bodies vary between tissue types¹⁵. A second difference between KE arises from the balance between direct delivery of ketones compared to indirectly elevating ketone concentration via metabolism of non-classical or classical ketogenic precursors (**Figure 1**). Classical ketogenesis itself may drive adaptation and some of the functional benefits associated with ketosis¹⁹. BDO is included in all of the KE compounds, but it is currently

unknown how consumption of BDO alone, and its metabolism via non-classical ketogenesis acutely affects metabolism. Additionally, ketogenesis is now understood to occur in certain cells outside the liver with important local biological effects, for example ketogenesis driven by medium chain fatty acids has been reported in astrocytes *in vitro*¹⁰. Provision of systemic BHB by a KE may elicit different biological effects in some tissues such as the brain versus promoting *in situ* ketogenesis in that tissue. Overall, not only are functional effects of KE incompletely defined, but also it is unknown which effects are common to all KE versus which are specific to an individual KE compound (i.e., BHB Monoester vs AcAc Diester) or which may be attributable to the BDO precursor common to all of the KE.

This study will be the first comparative full crossover study of all available KE and the precursor BDO at two serving sizes. Outcomes will focus on established effects of the BHB Monoester (including the effects on ketones, glucose and acid-base balance) and compare these with the effects of the AcAc Diester, C6 Diester and BDO. The results of this project will provide information to facilitate selection of exogenous ketones based on the specific physiological and metabolic effects that they induce.

[figure not shown]

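### The protocol aims to compare the ketone compounds with one another, but its analysis plan names no between-compound contrast

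*Protocol*

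**What the plan says.** The aim is in the Protocol, Summary and Background, in the paragraphs on how metabolic effects differ between compounds. They state: "This study will be the first comparative full crossover study of all available KE and the precursor BDO at two serving sizes". Next comes "Outcomes will focus on established effects of the BHB Monoester", with the intention to "compare these with the effects of the AcAc Diester, C6 Diester and BDO". The gap in knowledge is that "it is unknown which effects are common to all KE versus which are specific to an individual KE compound", or which effects may be due to the BDO they share. The results are meant to "facilitate selection of exogenous ketones based on the specific physiological and metabolic effects that they induce".

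The comparison rules are elsewhere:

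- **Outcomes (Research Strategy), footnote to the secondary outcomes:** "All comparisons will be made between the two serving sizes of one study product and vs. control".
- **Statistical Plan, comparison sentence:** "We will compare data between control group vs. each individual exogenous ketone at both doses". The example has three levels: control, BHB Monoester 180 mg/kg and BHB Monoester 360 mg/kg.
- **Statistical Plan, inclusion rule:** a participant's data count if both servings of one product and the control day were completed. A product with only one serving completed is left out.
- **Sample Size:** the goal is to "demonstrate significant differences between serving sizes of exogenous ketone compounds in plasma total ketone AUC".

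The repeated-measures ANOVA and Tukey sentences in the Statistical Plan do not list the conditions they cover.

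**The concern.** Whether an effect is shared by all compounds or belongs to one of them is a question about differences between compounds. The comparison rules cover differences from control and between servings of one product. The AUC estimates for each compound would be visible side by side, but no test or interval would attach to the difference between two of them.

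Separate verdicts against control do not fill the gap. For ketone AUC nearly every product should beat control, so those verdicts cannot tell compounds apart. For weaker secondary outcomes, one compound may reach significance and another miss it by chance, which misleads if it is read as a difference. The inclusion rule would also discard participants who have both days of a same-serving contrast but lack some other day.

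**Working it through.** **Contrasts.** Four compounds at two servings plus control make 9 conditions and C(9,2) = 36 pairs:

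| Type of pair | Number | In the Statistical Plan's three-level sets |
|---|---|---|
| Product vs control | 8 | 8 |
| Two servings of one product | 4 | 4 |
| Between compounds, same serving | C(4,2) × 2 = 12 | 0 |
| Between compounds, different servings | 12 | 0 |

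The aim names the BHB Monoester against three others, which is 3 × 2 = 6 of the 12 same-serving pairs. The count specified is again 0.

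**The plan's own figure.** 12 evaluable with 20% attrition gives 12/(1 − 0.20) = 15, as stated. The 12 cannot be reproduced because no SD is printed.

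**Precision of a between-compound contrast (illustrative).** Assume that the 12 came from a paired two-sided t-test with 80% power, that the printed alpha of 0.5 means 0.05, and that the earlier BHB AUC difference of about 20% carries over to total ketone AUC. Then the standardised difference is 0.889 and the SD of paired differences is 20/0.889 = 22.5% of AUC. With k contrasts tested at 0.05/k, and half-width t × 22.5/√12:

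| k | Power, n = 12 | Power, n = 15 | Detectable at 80% power, n = 12 | Half-width, n = 12 |
|---|---|---|---|---|
| 1 | 0.80 | 0.89 | 20.0% | 14.3% |
| 3 | 0.61 | 0.75 | 24.3% | 18.3% |
| 6 | 0.48 | 0.65 | 27.0% | 20.8% |

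Other readings of the 12 give this range (n = 12, three contrasts):

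| Reading | SD of paired differences | Power per contrast | Half-width, unadjusted (adjusted) |
|---|---|---|---|
| One-sided 0.05 | 26.1% | 0.47 | 16.6% (21.2%) |
| Unpaired, 12 per group, within-participant correlation 0 to 0.6 | 23.6% to 14.9% | 0.56 to 0.95 | 15.0% to 9.5% (19.2% to 12.2%) |
| Alpha literally 0.5 | 47% | 0.14 | 29.9% (38.3%) |

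**Ketone AUC against control.** Take two products with AUC 100 and 80 and a near-zero control. With the same SD of 22.5, the standardised differences are 100/22.5 = 4.44 and 80/22.5 = 3.55. Both beat control with over 99.9% power at n = 12, although they differ by 20%.

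**Opposite verdicts for two identical compounds.** If the two tests were independent with power p, the chance would be 2p(1 − p): 50% at p = 0.5 and 32% at p = 0.8. A shared control makes them agree more often. Simulation (60,000 replicates, n = 12, correlation 0 to 0.6) gives:

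| Control SD relative to products' | 50% power | 80% power |
|---|---|---|
| Equal | 35% | 23–24% |
| Half | 39–44% | 26–29% |
| One tenth | 33–50% | 23–32% |

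Repeating this with an ANOVA followed by Tukey, as the plan describes, gives about 34% at 48% power and 22% at 81%.

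**Inclusion rule.** A same-serving contrast needs 2 test days. Under the rule it needs 5: both servings of both products, and control.

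- If 5% of visits are missed at random (an assumption), usable n is 15 × 0.95² = 13.5 against 15 × 0.95⁵ = 11.6.
- If 3 of 15 drop out after a uniform 0 to 8 of 9 randomly ordered days, the chance of holding 2 given days is 84/(36 × 9) = 0.259, and of holding 5 given days 84/(126 × 9) = 0.074. Usable n is 12 + 3 × 0.259 = 12.8 against 12 + 3 × 0.074 = 12.2.

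**The case against.** The plan agrees with its own outcomes: the primary outcome, the sample-size goal and the Statistical Plan all concern serving sizes and control. The mismatch is with aim wording in the background, which promises a comparison but no formal test. This stands. No primary conclusion is at risk, and rewording the aim would be a legitimate cure.

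The ANOVA and Tukey sentences could also mean one nine-condition model with all 36 pairs, which would contain every between-compound contrast. The restrictive footnote hangs on the secondary outcomes only and is not repeated in the synopsis or the statistical section. This reading is possible but less likely: the reference to each individual product, the three-level example and the inclusion rule all point the other way. If it was intended, the text still needs correcting. Power per contrast under Tukey over nine conditions would be about 46%, on the same illustrative SD and equal variances.

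A full contrast list is normal SAP content. But this is a conflict rather than silence: for the secondary outcomes, an SAP that added between-compound contrasts would contradict the footnote.

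The power, discordance and missed-visit figures rest on assumptions, because the protocol prints no SD and no missed-visit rate. This too stands. With the protocol's own attrition, the inclusion rule costs only about half a participant per contrast. The count of zero depends on none of these figures.

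**Conclusion.** The point holds and should be fixed. The stated aim is to compare compounds, while the analysis text, on its natural reading, specifies 12 contrasts of which none is between compounds: 0 of 12 at the same serving, or 0 of the 6 that involve the BHB Monoester. That conclusion rests on the text and on counting. The consequences are illustrative. Opposite verdicts for identical compounds in about 35% to 24% of trials assume 50% to 80% power against control and equal SDs; the range is about 23% to 50% if the control SD is 0.1 to 0.5 of the products'. The power and interval widths assume an SD of paired differences of 22.5% of AUC.

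**What to change.** Either make the between-compound comparison part of the plan or stop promising it.

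1. Narrow the Outcomes footnote so that it no longer rules out between-compound comparisons.
2. In the Statistical Plan, keep the serving-size and control contrasts as primary.
3. Add a prespecified secondary set of same-serving, within-participant contrasts: BHB Monoester against C6 Di-ester, AcAc Di-ester and BDO. Report each as a paired difference with a confidence interval and a named adjustment, for example Holm over three contrasts at one serving named in advance, or over six if both are tested.
4. Give the remaining three pairs (C6 vs AcAc, C6 vs BDO, AcAc vs BDO) as estimates with intervals.
5. Use paired contrasts or a mixed model with condition-specific variances, since control ketone values may vary less than product values.
6. Include every participant who has both conditions of a contrast, and state that the product-by-product exclusion rule does not apply to this set.

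If no between-compound inference is wanted, reword the aim in the Summary and Background as a descriptive comparison.

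The cost is wording and a little more analysis, with no new data or participants. Because power is limited, the intervals rather than the significance tests should carry the between-compound result.
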